9.2 Setting

The registry setting is countries within and outside Europe where Increlex® is registered and marketed.

It is intended to collect safety data in children and adolescents receiving Increlex® therapy for SPIGFD according to the locally approved product information at sites experienced in the diagnosis and management of children and adolescents with SPIGFD in participating countries.

The aim is to enrol as many Increlex®-treated patients as possible into the registry at each participating site and the results should provide valuable information on the long-term risk of malignancies and other risks in a relatively large group of children and adolescents with this rare disease.

To be eligible for enrolment in the registry, participants must comply with all of the following inclusion and exclusion criteria:

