7.3 Rationale for the Registry

As the current knowledge of IGF-1 biology suggests that IGF-1 plays a role in malignancies in all organs and tissues, there is an increased risk of benign and malignant neoplasia in children and adolescents treated with Increlex®. In order to monitor the risk of neoplasms and other safety concerns such as metabolic or cardiovascular risk, and as part of the overall risk management strategy for Increlex®, the Marketing Authorisation Holder (MAH) put in place a post-authorisation safety surveillance registry in the EU, called the European Increlex® (Mecasermin [rDNA Origin] Injection) Growth Forum Database (EU-IGFD 2-79-52800-002) to monitor the safety and effectiveness of Increlex® therapy, with the Specific Obligation to investigate long-term safety until 5 years after the end of treatment for a subset of participants exposed for at least 3 years. The EU-IGFD registry was implemented at the end of 2008 in ten European countries with a MA approved for Increlex® under Exceptional Circumstances.

Recently, as a result of postmarketing safety surveillance activities, occurrences of benign and malignant neoplasia were observed among children and adolescents who received treatment with Increlex®. A safety signal was submitted to the EMA which concluded that the benefit-risk profile of Increlex® remains positive in its approved indication only, at doses not higher than the daily recommended doses. In May 2019, a Type II variation to update the EU Summary of Product Characteristics (SmPC), Risk Management Plan (RMP) and Additional Risk Minimisation Material was distributed in the EU and relevant global markets between December 2019 and July 2020.

Considering the identified risk of malignancies, the Specific Obligation to investigate long-term safety after the end of Increlex® treatment and the possible occurrence of malignancies as well as other risks, the MAH has decided:

- To geographically expand the current EU-IGFD registry to additional countries within and outside Europe where the product is registered and marketed, and;
- To collect long-term safety data after completion of treatment for all participants who have received treatment with Increlex®, regardless of duration of therapy.

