9.7 Data Analysis

9.7.1 Analyses Population Definitions

At the site level:

Screened: site which has been contacted for participation in the registry and confirmed that they are currently following patients who may be eligible for the registry (this includes both participating and non-participating sites).

Participating: site which has agreed to participate in the registry and has completed a patient screening log (as minimum data requested for participation).

At the patient/participant level:

Screened Population: all patients included in the patient screening log (this includes both enrolled and non-enrolled patients, with the reason for non-enrolment).

Enrolled Population: all participants who are fully informed about the registry and who have given their written informed consent to participate (and/or their parents/legally authorised representatives) before implementation of any registry-related procedure.

Registry Population: all participants who have completed at least one follow-up visit and who have taken the treatment at least once.

Complete Population: all participants who have stopped treatment and who have been followed until FAH reached.

Safety Population: all participants who have taken the treatment at least once and with at least one follow-up visit or presence of any post-study treatment safety data.

Long-term Safety Population: all participants who have been exposed to Increlex® for at least 3 years and who ended therapy at least 2 years prior to the collection of long-term safety data. The primary analysis based on the primary endpoint will be performed on the Safety Population.

9.7.2 *Statistical and Analytical Methods*

9.7.2.1 *Statistical Analyses*

The statistical analyses will be performed by an external SP managed by the Sponsor.

A Statistical Analysis Plan (SAP) describing the planned statistical analysis in detail with tables, figures and listings templates will be developed as a separate document.

Statistical evaluation will be performed using Statistical Analysis System (SAS)[®] (Version 9 or higher).

As this is a non-interventional study, no formal statistical testing will be performed and all the analyses will be primarily descriptive in nature. When appropriate and unless otherwise specified, 2-sided 95% confidence intervals (CIs) will be displayed and if p-values are presented, they will be for exploratory purposes only.

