Descriptive statistics will include number of available data, number of missing data and the following:

- Mean, SD, 95% CIs for means when appropriate, median, quartile, minimum and maximum for continuous variables;
- Frequency count, percentages and 95% CIs when appropriate for categorical nominal variables;
- Both the above for categorical ordinal variables.

Missing data will not be replaced but they will be displayed in all relevant tables.

9.7.2.2 *Participant Inclusion*

Based on the screened population, the proportion of non-included patients will be assessed as well as the reasons for non-inclusion.

9.7.2.3 *Demographic and Other Baseline Characteristics*

Descriptive statistics of demographic and baseline data will be presented for the Registry Population.

Previous/concomitant medications will be summarised by drug categories.

Data on medical history, coded using MedDRA, and previous growth therapy will be summarised.

Information on SPIGFD diagnosis, personal or familial risk factors for neoplasia and genetic test results (deletion/mutation of GH gene, IGF-1 gene, FGF, PTPN11, GHR, D3-GHR, STAT5b, ALS, SHOX, PAPPA2 and any other genetic tests performed, e.g. whole exon sequencing) will be described.

9.7.2.4 *Participant Disposition and Withdrawals*

The numbers and percentages of participants included in the analysis populations will be tabulated overall and by country and site. The reasons for participant exclusions from each of the populations will also be tabulated.

In addition, the number of participants who ended the treatment, withdrew or completed the registry will be presented with the primary reasons for discontinuation.

9.7.2.5 *Primary Analyses*

The primary analyses and summary tables of safety data will be based on the Safety Population (data from the treatment period only).

An overall summary table of AEs during the treatment period (up to 30 days after the last dose) including SAEs, AESI, targeted AEs, all AEs, AEs leading to death and AEs leading to withdrawal will be presented with the number and proportion of participants and the number of events.

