All treatment emergent AEs (TEAEs) will be coded according to MedDRA and will be classified by MedDRA primary system organ class (SOC) and preferred term (PT). The incidence of all TEAEs, SAEs, AESI, targeted AEs, AEs leading to death and AEs leading to withdrawal will be tabulated by primary SOC and PT. In addition, summary tables by maximum intensity and drug relationship will be presented.

AE listings will be presented by participant, primary SOC and PT.

The relationship of frequently occurring AEs, e.g. hypoglycaemia, to prognostic variables such as age, pubertal status, and dose will be explored.

All primary safety data will also be included in the participant data listings.

9.7.2.6 *Secondary Analyses*

Safety Analyses

The secondary safety analyses will be based on the Safety Population. Adverse event data are from the post-treatment period only but data on special situations and concomitant medications are from the treatment and post-treatment periods.

An overall summary table of AEs occurring during the post-treatment period (over 30 days after the last dose) including SAEs, AESI, targeted AEs, all AEs and AEs leading to death will be presented with the number and proportion of participants and the number of events.

The incidence of all post-treatment AEs, SAEs, AESI, targeted AEs and AEs leading to death will be tabulated by MedDRA primary SOC and PT. In addition, summary tables by maximum intensity and drug relationship will be presented.

The same analyses will be performed in a subset of children and adolescents exposed to Increlex® for at least 3 years.

Post-treatment AE listings will be presented by participant, primary SOC and PT.

An overall summary table of special situations occurring during the treatment and post-treatment periods will be presented with the number and proportion of participants and the number of events. For the post-treatment period, the same analyses will be performed in a subset of children and adolescents exposed to Increlex® for at least 3 years.

Concomitant medications during the treatment and post-treatment periods will be tabulated.

Incidence of neoplasia (benign and malignant) and hypoglycaemia will be presented according to the timeframe of occurrence (e.g. within the first 3 years after start of treatment, between 3 and 5 years and over 5 years).

All secondary safety data will also be included in the participant data listings.

Effectiveness Analyses

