3.2 Does the protocol specify whether the study is based on primary, secondary or combined data collection?				9.4
3.3 Does the protocol specify measures of occurrence? (e.g. incidence rate, absolute risk)				N/A
3.4 Does the protocol specify measure(s) of association? (e.g. relative risk, odds ratio, excess risk, incidence rate ratio, hazard ratio, number needed to harm (NNH) per year)				N/A
3.5 Does the protocol describe the approach for the collection and reporting of adverse events/adverse reactions? (e.g. adverse events that will not be collected in case of primary data collection)				11
Comments: This is a descriptive study therefore no formal statistical testing will be performed and the analyses will be primarily descriptive.				

Section 4: Source and study populations	Yes	No	N/A	Section Number
4.1 Is the source population described?				9.2.3
4.2 Is the planned study population defined in terms of:				
4.2.1 Study time period?				9.2.4
4.2.2 Age and sex?				9.2.1
4.2.3 Country of origin?				9.2.5
4.2.4 Disease/indication?				9.2.1
4.2.5 Duration of follow-up?				9.2.4
4.3 Does the protocol define how the study population will be sampled from the source population? (e.g. event or inclusion/exclusion criteria)				9.2.1
Comments: The study will be conducted in countries within and outside Europe where Increlex® is registered and marketed.				

Section 5: Exposure definition and measurement	Yes	No	N/A	Section Number

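### The planned neoplasia tables describe occurrence in treated children but give no person-time rate or expected number, so they cannot by themselves show whether malignancies are in excess

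*Protocol*

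**What the plan says.** **Purpose.** Section 7.3 gives the reason for the registry: "In order to monitor the risk of neoplasms and other safety concerns such as metabolic or cardiovascular risk". The same section states that "there is an increased risk of benign and malignant neoplasia in children and adolescents treated with Increlex". Section 9.2 adds that "the results should provide valuable information on the long-term risk of malignancies and other risks". The end of section 9.9 also expects the registry to let the sponsor measure how well the additional risk minimisation measures work, neoplasias in particular.

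**Planned output.** For the treatment period, section 9.7.2.5 says of the overall adverse event table, which covers AESI (all neoplasias), that results "will be presented with the number and proportion of participants and the number of events". It then says: "The incidence of all TEAEs, SAEs, AESI, targeted AEs, AEs leading to death and AEs leading to withdrawal will be tabulated by primary SOC" and preferred term. Section 9.7.2.6 repeats this for the post-treatment period and adds: "Incidence of neoplasia (benign and malignant) and hypoglycaemia will be presented according to the timeframe of occurrence", with example bands of up to 3, 3 to 5 and over 5 years from start of treatment. Section 9.7.2.1 provides for two-sided 95% CIs when appropriate and states that "no formal statistical testing will be performed and all the analyses will be primarily descriptive in nature".

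**Reference level.** The protocol has no comparator group, population rate, expected count or person-time denominator. In Appendix 2, checklist item 3.3 (measures of occurrence, with incidence rate as an example) is marked N/A. So is item 3.4, "Does the protocol specify measure(s) of association".

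**The concern.** Neoplasia is the risk that prompted the registry and its global expansion. Some malignancies will occur by chance in any cohort of this age range followed long enough. A count or proportion from a treated-only cohort therefore needs two more things before it says anything about excess: how much follow-up produced it, and how many cases that follow-up would produce anyway. The planned tables give neither directly.

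Follow-up will also differ widely between participants. Treatment duration is at the physician's discretion, post-treatment follow-up is at least 5 years and longer if adult height is not reached, and losses and withdrawals occur. A simple proportion treats all of these participants alike.

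At stake is how the interim reports and the DMC's periodic review can interpret the neoplasia tables. Section 9.9 warns that the non-randomised design may not allow the lowest effective dose to be determined. It gives no comparable warning for malignancy, where the lack of a comparator also limits the conclusions.

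**Working it through.** **Inputs from the protocol.** All participants are treated (9.2.1). Post-treatment follow-up is at least 5 years on top of the treatment period (9.2.4.3). Section 9.5 gives no target number. The only size figure is the earlier commitment of 100 subjects treated for at least 3 years (9.9). No expected count or reference rate is stated, so there is no figure of the plan to reproduce.

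**Assumptions, not in the protocol.** Background malignancy incidence of 100 to 300 per million person-years (PY); average follow-up of 5 or 8 years; a larger registry of 300 participants.

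**Formulas.** Expected E = PY × rate. Ratio = O/E. Exact 95% limits for a Poisson count O are χ²(0.025; 2O)/2 and χ²(0.975; 2O+2)/2; for O = 2 these are 0.242 and 7.22. P(X ≥ 2) = 1 − e^(−E)(1 + E).

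**Step 1: a proportion does not carry follow-up time.** Two cases in 100 participants print as 2/100 = 2.0% (exact 95% CI 0.2 to 7.0%).
- 100 × 5 = 500 PY: 2/500 = 4.0 per 1,000 PY (0.48 to 14.4).
- 100 × 8 = 800 PY: 2/800 = 2.5 per 1,000 PY (0.30 to 9.0).

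The proportion is the same in both cases.

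**Step 2: a proportion does not carry a reference.** Two cases in 300 participants print as 2/300 = 0.67% (exact 95% CI 0.08 to 2.4%). With 300 × 8 = 2,400 PY:

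| Assumed rate per million PY | E | O/E (95% CI) | P(X ≥ 2) |
|---|---|---|---|
| 100 | 0.24 | 8.3 (1.0 to 30.1) | 0.025 |
| 200 | 0.48 | 4.2 (0.5 to 15.1) | 0.084 |
| 300 | 0.72 | 2.8 (0.3 to 10.0) | 0.163 |

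One printed line covers a count that looks raised and a count compatible with no excess.

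**Step 3: the protocol's own size figure.** With 100 subjects:
- 500 PY: E = 0.05 to 0.15. Two cases give O/E from 40 (4.8 to 144.5) down to 13.3 (1.6 to 48.2).
- 800 PY: E = 0.08 to 0.24. Two cases give O/E from 25 (3.0 to 90.3) down to 8.3 (1.0 to 30.1).
- P(X ≥ 2) runs from 0.001 to 0.025 across these, so at this size two cases look raised throughout the assumed range.
- Zero cases in 500 PY still leaves an upper O/E limit of 3.69/0.15 = 24.6 to 3.69/0.05 = 73.8.

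**Step 4: a wider range.** At 250 × 8 = 2,000 PY and 100 per million, E = 0.2. Two cases then give O/E 10 (1.2 to 36.1), P = 0.018. At 500 × 10 = 5,000 PY and 250 per million, E = 1.25. Two cases then give O/E 1.6 (0.2 to 5.8), P = 0.36. Here the planned table would not look identical: it would show 2/250 = 0.8% and 2/500 = 0.4%. Neither percentage reveals which situation applies.

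**The case against.** The strongest reply is that the protocol promises no comparison. Its objectives are to collect and describe safety data (8.2), formal testing is ruled out (9.7.2.1), and the comment to checklist section 2 says there is no prior hypothesis. The sentence in 9.2 is general text, and absolute occurrence in a rare treated group is itself useful. This stands. A reader might infer that the protocol contradicts its objectives, but none of them asks whether malignancy exceeds population rates.

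A reader might also infer that malignancies are merely counted. They are not: proportions, intervals when appropriate and time bands are planned. Treatment duration and duration of post-treatment follow-up are summarised too (9.7.2.6), so person-years could be approximated.

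A third tempting inference is that no signal could emerge. The documents do not support that either. Neoplasias are reported within 24 hours (11.1.6) and followed with a dedicated questionnaire (11.2.4). Investigators assess causality (11.3.1). Safety data are analysed every 6 months and reviewed by an external DMC at least yearly (9.7.4). Section 7.3 records that postmarketing surveillance has already produced a neoplasia signal.

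It can be said that an observed/expected table belongs in the SAP, which is not at hand, and that N/A on a checklist forbids nothing. That is only partly persuasive. Marking both occurrence and association as not applicable goes further than leaving them open, and the choice of a reference is a design matter.

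Finally, the general population is a poor stand-in for untreated SPIGFD, and precision will be low. Both are true and should be stated as limits. They do not make a bare proportion more informative.

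**Conclusion.** The point holds as a cheap improvement to an openly descriptive plan. The planned tables report how often neoplasia occurred. Without person-time and an expected number, they cannot by themselves tell an excess of malignancies from what age, sex and length of follow-up would produce. Case-level review remains able to raise a signal.

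The size can only be illustrated. In the assumed 2,400 PY, the same two cases range from O/E 8.3 to 2.8 as the background rate goes from 100 to 300 per million. At the 100-subject figure in 9.9 they look raised throughout that range. How ambiguous a small count is therefore depends on the registry's actual size, follow-up and reference rates, none of which the protocol gives. That a proportion carries neither person-time nor a reference does not depend on these assumptions.

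**What to change.** Add to section 9.7.2.6, and to the DMC package, as a descriptive statistic for first malignant neoplasms after enrolment, kept separate from benign ones:

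- the observed number;
- person-years from enrolment to first malignancy, death, withdrawal or last contact;
- the rate per person-years;
- the expected number, from population cancer incidence by age, sex, country and calendar period;
- O/E with an exact Poisson 95% CI, for the treatment and post-treatment periods combined and split.

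Starting at enrolment matters because participants already on treatment may join with retrospective data (9.1) and had to be free of active or suspected neoplasia to do so (9.2.2).

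Update checklist items 3.3 and 3.4. In section 9.9, state that:

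- the general population is not an untreated SPIGFD population;
- eligibility differs by region and era: the EU exclusion covers conditions that raise neoplasia risk, the US list names only active or suspected neoplasia, and off-label patients from before Amendment 6 may remain in follow-up;
- intervals will be wide.

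The cost is protocol wording, programming and obtaining population cancer rates. Sex, month and year of birth, country, dose dates, visit dates, and dates of death and withdrawal are already recorded, so no new participant data and no test are needed. The drawback is an imperfect reference with low precision, so the ratio should be read as context for the case review and not as an estimate of a treatment effect.

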9.2.1 Inclusion Criteria

(2) Children and adolescents from 2 to 18 years:

- For US, patients starting or planning to start or currently receiving treatment with Increlex® therapy for severe primary IGF-1 deficiency as defined by the US Increlex® prescribing information or for growth hormone (GH) gene deletion who have developed neutralizing antibodies to GH.
- For EU, patients starting or planning to start or currently receiving treatment with Increlex® therapy according to the locally approved product information. Note:

not applicable for patients enrolled in the EU-IGFD registry and entering or currently in the post-treatment period.

(2) Signed informed consent as per local regulations needs to be obtained. Parents or legally authorised representatives if applicable must give signed informed consent before any registry-related activities are conducted. Assent from the participant should also be obtained as appropriate.

9.2.2 *Exclusion Criteria*

(1) Patient currently participating in an Increlex® clinical trial.

(2) Patient currently participating in any clinical trial for growth retardation.

(3) Patient with any contraindication to Increlex® or any condition subject to special warning as per the locally approved label.

- For US patients, these include patients with hypersensitivity to the active substance or any of the excipients, patients with active or suspected neoplasia and patients with closed epiphyses.
- For EU patients: these include patients with hypersensitivity to the active substance or any of the excipients, patients with active or suspected neoplasia or any condition or medical history which increases the risk of benign or malignant neoplasia and patients with closed epiphyses. Note: not applicable for patients enrolled in the EU-IGFD registry and entering or currently in the post-treatment period.

Note: for any patients enrolled in the registry under previous inclusion/exclusion criteria (i.e. before implementation of Protocol Amendment #6), who would be ineligible according to any of the above inclusion or exclusion criteria, e.g. receiving Increlex® for an indication not covered by the locally approved product information, a letter will be sent to the Investigator to alert him/her about the off-label use of the product (specifically for the risk of neoplasias). The patient could continue to be followed up in the registry for safety data in the post-treatment period.

9.2.3 *Registry Population*

9.2.3.1 *Physician Profile*

Eligible Investigators for the global registry will be:

- Physicians who are experienced in the diagnosis and management of children and adolescents with SPIGFD;
- Physicians located in a country where Increlex® is approved and marketed and where the study is implemented;
- Physicians who have prescribed/plan to prescribe Increlex® according to the locally approved product information.

9.2.3.2 *Participant Population*

Eligible participants will be children and adolescents from 2 to 18 years starting or planning to start or currently receiving treatment with Increlex® therapy for SPIGFD according to the locally approved product information in participating countries. In order to be enrolled, participants must comply with all the inclusion criteria (Section 9.2.1) and exclusion criteria (Section 9.2.2).

9.2.3.3 *Patient Screening and Number of Participants*

The current global Increlex® registry should be proposed to all eligible Increlex®-treated patients at the site.

During screening, Investigators must explain the purpose of the registry as well as the identified risk of neoplasia and the need to be followed up until at least 5 years after the end of treatment. Investigators must give the Participant Information Sheet (PIS) to the participant (and/or the participant's parents or legally authorised representative) which summarises all information related to the study given by Investigators:

- If participation in the registry is confirmed (the participant/parents or legally authorised representative agree to participation), the informed consent will be discussed and signed (before any related data collection) and the enrolment visit will be recorded.
- If the patient is not participating in the registry, registration date and reason for non-participation should be recorded in the eCRF in order to assess the proportion of non-included patients, only if the patient has no objection to this data collection.

A unique number will be attributed to each participant enrolled, to be used throughout the registry.

9.2.4 *Registry Duration*

9.2.4.1 *Recruitment Period*

This is an ongoing open-ended registry. Enrolment in the EU-IGFD registry started in December 2008.

For each new participating site/country, enrolment will start following local site initiation with all necessary regulatory and ethics local approvals.

9.2.4.2 *Treatment Duration*

For each participant, Increlex® treatment duration is at the discretion of the treating physician according to his/her clinical judgment and according to the locally approved product information.

9.2.4.3 *Follow-up Duration*

The registry will cover a post-treatment follow-up period of at least 5 years in addition to the treatment period for all enrolled participants regardless of treatment duration, for which the study Investigator is also responsible.

If the participant has not reached the FAH at the end of 5-year post-treatment period, the follow-up period will be extended up to the achievement of the FAH.

9.2.5 *Registry Place*

Countries within and outside Europe where Increlex® is registered and marketed.

9.2.5.1 *Site Selection*

In each participating country, sites who are experienced in the diagnosis and management of patients with SPIGFD will be contacted to perform a site feasibility assessment. Sites will be selected to participate in the study if they meet the study requirements. Site selection may be conducted by a Service Provider (SP) directed by the Sponsor. All procedures will be completed in accordance with the Sponsor and the contracted SP's Standard Operating Procedures (SOPs).

Considering that the objective of this registry is to enrol the maximum possible number of Increlex® treated patients in each participating country, the number of sites will not be limited to a maximum per country.

Investigators must be informed about the importance of the follow-up visits including at least visits at years 2 and 5 after the end of treatment, and it should be emphasised that they need to inform potential patients and/or parents/legally authorised representatives of the importance of attending these visits.

